## 6.5 Safety Rationale

The major risks of PDM608 administration to humans are excessive pharmacology of stimulation of GM-CSF activity and the consequences of development of ADA against the product. The pharmacology of GM-CSF is outlined in the Investigator's Brochure. Common AE in clinical studies with sargramostim include injection site reactions, headache, bone pain, flu-like symptoms and increased blood leukocyte levels (Leukine USPI). This protocol specifies white count as an adverse event of special interest ([Section](#)

---

13.5). This protocol allows the use of acetaminophen if the Investigator believes it is appropriate to manage AE (Section 11.3). Sargramostim, a yeast derived GM-CSF, has been associated with the development of ADA, but there is little evidence that these antibodies result in AE, and the evidence that they reduce pharmacological activity of sargramostim is mixed (see the Investigator's Brochure). PDM608 is designed to have low immunogenicity in humans. This protocol will measure ADA with a validated assay. Serum sickness-like reactions, which may be a consequence of ADA, will be monitored through vital signs, laboratory safety testing and AE. This protocol instructs the Investigator to contact the Sponsor if a rash develops that may be part of a serum sickness-like reactions (Section 13.5).

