### 10.3.6 Follow-up

If a subject reports any AEs that can present a cause for concern, they will be required to attend the clinical unit for a further follow-up assessment (as an unscheduled visit) and will be followed up until the AE has resolved. Completion of the last scheduled return visit or unscheduled follow-up call/visit will be considered the end of the study.

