### 13.3 Recording Adverse Events

AEs will be recorded from the time of providing written informed consent until 30 days after the last dose of study drug. During each study visit the subject will be questioned directly regarding the occurrence of any adverse medical event according to the schedule in eCRF. All AEs, whether ascribed to study procedures or not, will be documented immediately in the subject's eCRF. This will include the date and time of onset, a description of the AE, severity, seriousness, duration, actions taken, outcome and an investigator's current opinion on the relationship between the study drug and the event. A diagnosis and final opinion on the relationship between the study drug and the event will be provided at the end of the study by the investigator.

Any subject who withdraws from the study due to an AE will be followed until the outcome is determined and written reports are provided by the investigator.

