#### **13.5 Adverse Events of Special Interest (AESI)**

The following AESI must be reported to the Sponsor within 24 hours of site awareness irrespective of seriousness, severity or causality:

- Serum sickness-like reaction – a type III hypersensitivity reaction presenting with a constellation of symptoms including fever, pruritic rash, joint pain/tenderness/edema/erythema, muscle pain, edema of the lips and/or eyelids, GI symptoms (nausea, vomiting, abdominal cramps, diarrhea), headache and dyspnea
- A new vasculitic rash, a fixed, erythematous, non-blanching rash. Vasculitic rashes may be accompanied by fever, fatigue and diffuse aches or pain
- Urticarial reaction
- Leucocytosis with WBC > 50,000/uL

In the event of a suspected serum sickness-like reaction blood samples will be collected within 1 hour of the event to assess CBC, ESR, urinalysis, serum chemistries, C3, C4 and fibrinogen.

The subsequent course of therapy may include NSAIDs, antihistamines and/or corticosteroids depending on institutional guidelines and the severity of the event.

The investigator is encouraged to discuss with the Sponsor medical monitor all AESI as defined above.

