### **13.7 Vital Signs Measurements**

Blood pressure and heart rate will be measured by an automated recorder after the subject has been in a supine position for a minimum of 5 minutes and body temperature and respiratory rate will be measured according to the Schedule of Assessments presented in [Appendix 2](#) (Part 1) and [Appendix 3](#) (Part 2). The acceptable deviations from the nominal vital signs assessment times are detailed in the schedules.

If a subject shows an abnormal assessment at any stage, repeat measurements may be made and the abnormality followed to resolution if required. Additional measurements may be taken as deemed necessary by the investigator or sub-investigator.

Any clinically significant abnormality, including changes from baseline, must be reported as an AE.

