### **13.11 Additional Safety Procedures**

Additional non-invasive procedures that are already specified in the protocol may be performed if it is believed that an important effect of the IMP is occurring, may occur at a time when no measurements are scheduled or if extra procedures are needed in the interests of safety.

Additional blood samples, urine samples or other diagnostic tests for safety assessments may be taken if required by the investigator or sub-investigator at any point.

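### Part 1, low-cost improvement: no vital signs, and so no temperature, appear to be scheduled at the return visits after Day 8, although Section 6.5 names vital signs as a channel for detecting serum sickness-like reactions

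*Combined protocol and SAP*

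**What the plan says.** Section 6.5 names two major risks: excessive GM-CSF pharmacology and the consequences of ADA. On the second it says: "Serum sickness-like reactions, which may be a consequence of ADA, will be monitored through vital signs, laboratory safety testing and AE".

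Section 13.5 makes this reaction an adverse event of special interest (AESI), described as "a type III hypersensitivity reaction presenting with a constellation of symptoms including fever, pruritic rash", followed by joint, muscle, gastrointestinal and other symptoms. Fever is listed first.

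Section 13.7 leaves the timing of temperature to the schedule: "body temperature and respiratory rate will be measured according to the Schedule of Assessments presented in" Appendix 2 for Part 1. Footnote h of Appendix 2 makes temperature part of vital signs, and no other row of that table carries it.

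In Appendix 2, subjects are resident from Day -1 to Day 8 and return on D11, D15 and D22. The vital-signs row is marked through the resident period and again in the last cell. It is blank in the three cells that hold the return-visit (RV) marks. The ADA row is marked in two of those three cells.

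**The concern.** Section 6.5 relies on three channels. One of them appears to have no scheduled reading after discharge, and the two later return visits are the ones at which ADA is sampled. A fever that the subject reports can still be recorded as an adverse event. No scheduled measurement would confirm it, or pick up one the subject had not noticed. The AESI work-up in Section 13.5 starts only once a reaction is suspected, so an objective temperature could help to raise that suspicion.

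Change from baseline in vital signs is also among the primary endpoints in Section 7. On this schedule the endpoint would have no planned late value in Part 1 for subjects who complete as planned.

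**Working it through.** The plan gives no figure to reproduce. The check is a reading of Appendix 2 followed by simple counts.

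**1. Columns.** Screening 1 + Day -1 1 + Day 1 5 (pre-dose, 0, 1, 3 and 12 h) + D2 to D8 7 + D11, D15, D22 3 + premature discontinuation 1 = 18. The text copy has 17 cells in each row, so one cell is missing.

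**2. Marked cells, as they stand.**

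| Row | Marked cells |
|---|---|
| Vital signs | 1–3, 7–13, 17 |
| ADA | 3, 13, 15, 16, 17 |
| Hematology/chemistry | 1, 2, 8, 9, 10, 12, 14, 16, 17 |
| Single ECG | 1, 2, 15, 16, 17 |
| RV | 14, 15, 16 |
| ±24 h windows | 14, 15, 16 |

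**3. Where the missing cell could be.** Let it fall at column k.
- k = 1 to 14 (screening to D8): vital signs are blank at D11, D15 and D22. RV falls on exactly those three days.
- k = 15: D11 is unknown; D15 and D22 are blank.
- k = 16: D15 is unknown; D11 and D22 are blank.
- k = 17: D22 is unknown; D11 and D15 are blank.
- k = 18: D22 is marked; D11 and D15 are blank.

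No single visit is blank at all 18 positions, but at least two of the three are blank at every position.

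**4. Which alignment.** For k = 15 to 18 an RV mark lands on D8, when subjects are still resident. For k = 1 to 14 the RV marks and the ±24 h windows both sit on D11, D15 and D22, which agrees with the study-day header. That reading is preferred.

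**5. Return visits on that reading.**

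| | Vital signs | Hematology/chemistry | AE questioning | ADA | Single ECG |
|---|---|---|---|---|---|
| D11 | no | yes | yes | no | no |
| D15 | no | no | yes | yes | yes |
| D22 | no | yes | yes | yes | yes |

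Physical examination and urinalysis are also unmarked at all three visits. The statement that D15 has only AE questioning sets aside the ADA sample itself, which Section 13.6.2 files under safety laboratory measurements.

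**6. Counts (full cohorts, no replacements).**
- PDM608 subjects: 5 × 6 = 30.
- Visits without a scheduled temperature: 30 × 3 = 90. With an ADA draw (D15, D22): 30 × 2 = 60.
- Minimum visits without a scheduled temperature, over all 18 positions: 30 × 2 = 60.
- Time from D8 to the last visit: (504 − 168)/24 = 14 days.
- Extra readings, all subjects because the study is blinded: 40 × 3 = 120; at the 50-subject maximum in Section 8.4, 50 × 3 = 150.

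**The case against.** The strongest reply is that nothing is broken. Section 6.5 names channels for the study as a whole and does not promise each one at each visit. Vital signs are taken through residency, laboratory tests are marked at D11 and D22, and adverse events are collected throughout. That stands: a reader might infer a contradiction between Section 6.5 and Appendix 2, and the documents do not support it.

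Nor are subjects unmonitored after discharge. Section 13.3 says: "During each study visit the subject will be questioned directly regarding the occurrence of any adverse medical event". Under Section 10.3.6, if an event gives cause for concern, "they will be required to attend the clinical unit for a further follow-up assessment". Section 13.7 adds: "Additional measurements may be taken as deemed necessary by the investigator or sub-investigator". Section 13.11 allows extra non-invasive procedures when an important effect "may occur at a time when no measurements are scheduled". A suspected reaction triggers blood tests within an hour and a report to the sponsor within 24 hours (Section 13.5). Section 8.2.1 lets the safety advisory committee, or the sponsor alone, change safety time points as data emerge. All of this stands. What it does not supply is a reading that needs no prior suspicion.

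The benefit is also limited. Most of the listed symptoms are ones a subject would notice. A spot temperature can miss an intermittent fever, and the acetaminophen permitted in Section 11.3 could blunt it. On antibodies to sargramostim, Section 6.5 says "there is little evidence that these antibodies result in AE", and it describes PDM608 as designed for low immunogenicity. These points lower the priority without removing the case for a nearly free measurement.

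Finally, the table text is imperfect. The header rows are short in different places, so rows need not have lost the same cell. If the vital-signs row lost its last cell and the ADA row an earlier one, only D15 would combine an ADA draw with blank vital signs. The figure of 60 ADA visits is therefore claimed only on the preferred alignment. The three blanks do coincide exactly with the RV cells, which makes chance loss an unlikely explanation.

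**Conclusion.** The point holds as a modest, low-cost improvement to Part 1. On the best-supported alignment, no vital signs are scheduled at D11, D15 or D22. That is 90 attended visits in 30 PDM608 subjects, 60 of them with an ADA draw, over the 14 days after Day 8. This assumes full cohorts, no replacements, one missing cell per row and no dropped marks. The printed table in the protocol can settle the alignment.

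Three stronger inferences are not supported:
- **The counts as a measure of risk.** They are visits without a reading. The documents give no rate for the reaction, so no number of missed events follows.
- **The monkey ADA timing.** Section 5.3.1.1 reports ADA from 336 through 672 hours, and in Part 1 336 h is D15. That study gave repeated weekly doses, so it does not fix the timing after a single dose.
- **The same gap in Part 2.** Appendix 3 also looks blank late in follow-up, but its text is too damaged to rely on. For example, hematology is blank from D22 to D29 although the synopsis requires it to 96 hours after Dose 4 for evaluability. No claim is made about Part 2.

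**What to change.** Mark vital signs, including body temperature, at D11, D15 and D22 in Appendix 2.

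This needs three marks in one row and a few minutes at visits subjects already attend, with no new visit and no extra blood: 120 readings in 40 subjects, at most 150. At D15 and D22 a single ECG is already marked on the preferred alignment. Sections 13.7 and 13.8 require the same five minutes supine, and Section 10.3.2 already puts the ECG before vital signs, so the added burden there is very small.

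The downside is an occasional incidental abnormal reading that has to be repeated or followed up.

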## 6.6 Risks and Benefits

### 6.6.1 Risks Associated with PDM608 Administration

Human data have yet to be generated for PDM608. However, over 30 years of clinical data for sargramostim suggests that GM-CSF is safe and well-tolerated. Please see the IB for details of risks and benefits of PDM608 administration.

### 6.6.2 COVID-19 Related Risks and Risk Mitigation Measures

The following risks and risk mitigating measures apply to the time in which the study is conducted during the Coronavirus Disease 2019 (COVID-19) pandemic.

#### 6.6.2.1 IMP Related Risk

Against the background of the COVID-19 pandemic, the potential risk of a subject developing COVID-19 has been considered in terms of the risk-benefit evaluation. The mode of action of the IMP – as a GM-CSF agonist – has been considered alongside available nonclinical and clinical data (including class effects) and it is considered that a subject would not be at increased risk of either becoming infected with severe acute respiratory syndrome coronavirus 2 (SARS-CoV-2; the virus that causes COVID-19) or experiencing a more severe illness. That is, the IMP has no known immunomodulatory effect that would confer an increased risk to healthy subjects enrolled in the study.

#### 6.6.2.2 General COVID-19 Related Risks and Risk Mitigation Measures

General risk mitigation against COVID-19 will be implemented in accordance with Quotient's monitoring and prevention control measures.

The risk mitigation measures, where applicable, will be amended based on emerging government guidance.

#### 6.6.2.3 COVID-19 Vaccine-Related Risk

Approved (including health authority conditional marketing authorization) COVID-19 vaccines (e.g., killed, inactivated, peptide, DNA and RNA vaccines) may be permitted according to the investigator's discretion and as per local guidance.

Based on the mechanism of action of the IMP, as a GM-CSF agonist, there is no perceived impact on the safety of the study subjects or on the study objectives for subjects who may receive these vaccines. It is also anticipated to be very unlikely that administration of the IMP would interfere with COVID19 vaccination response; however, no specific preclinical or clinical investigations have been conducted at this point with

PDM608. Therefore, no COVID-19 vaccines will be permitted within 14 days prior to first dose until a subject's final visit on this trial, and COVID19 vaccinations are not acceptable concomitant medications.

### 6.6.3 General Risks and Overall Risk-Benefit Assessment

PDM608 shares its mechanism of action with GM-CSF, sargramostim. The safety of sargramostim in various populations including healthy volunteers is outlined in the Investigator's Brochure. Flu-like symptoms and injection site rash were reported with a dose of 5-10 mcg/kg/day in these studies, while GM-CSF at 15 mcg/kg/day was not tolerated by donors, with 2 of 21 donors experiencing fever, chills and capillary leak syndrome (Devine 2005). This protocol allows the Investigator to manage headache, bone pain and flu-like symptoms as described in [Section 11.3](#).

Therapeutic proteins may cause the development of ADA, which might cause AE(s). Antibodies to GM-CSF have been associated with loss of pharmacodynamic activity in humans, but not with an increase in adverse events. ADA to GM-CSF have been shown to clear with time ([Ragnhammar 1994, Leukine package insert](#)).

Collecting a blood sample from a vein may cause pain, swelling, bruising, lightheadedness, fainting and, very rarely, clot formation, nerve damage and/or infection at the site of the needle stick.

Electrocardiogram (ECGs) stickers on the subjects' chests and limbs may cause some local irritation and may be uncomfortable to remove but subjects will be closely monitored to ensure any local irritation does not persist.

There is no anticipated clinical benefit to the subjects taking part in this study. The development of a product to treat neurodegenerative, autoimmune and oncological diseases may be of benefit to future patients.

The overall risk benefit balance is considered to be acceptable.

## 7 Objectives and Endpoints

Objectives	Endpoints
Primary	
To assess the safety, tolerability and PK of single (Part 1) and multiple (Part 2) SC doses of PDM608	
 
Incidence of AEs, change from baseline for physical examinations and vital signs, electrocardiograms (ECGs) and laboratory safety tests including ADA in blood
 
PK parameters for PDM608
 

Secondary	
To assess immunogenicity following single and multiple doses of PDM608	Incidence of ADA in blood
Exploratorya	
To assess PD following administration of single (Part 1) and multiple (Part 2) ascending SC doses of PDM608	
 
Individual baseline corrected leukocyte, Treg and other immune cell numbers/percentages
 
Individual baseline corrected cytokine levels
 

a Exploratory PD biomarker objectives may be reported separately to the Clinical Study Report.

## 8 Study Design

### 8.1 Study Plan

This is a 2-part, single-center, first-in-human study of SAD (Part 1) and MAD (Part 2) doses of PDM608 in healthy adult subjects. The 2 parts are not required to be conducted entirely sequentially provided that this is justified by safety data obtained from completed cohorts. The first MAD cohort will not be dosed until a minimum 3 SAD cohorts have undergone review by the SAC, and dosing for each MAD cohort will be at a dose level 2-3 fold lower than the highest SAD cohort dose deemed safe by the SAC at the time of each MAD cohort initiation.

#### 8.1.1 Study Plan: Part 1 Single Ascending Doses

Part 1 is a double-blind, randomized, placebo-controlled assessment of SC PDM608 SAD administrations. Subjects will be enrolled sequentially into 1 of up to 5 cohorts, each containing 8 subjects. Within each cohort, 6 subjects will be randomly assigned to receive PDM608 and 2 subjects will be randomly assigned to receive matching placebo. An evaluable subject for Part 1 is defined as a subject who has received the IMP dose and undergone all safety and tolerability assessments (inclusive of all scheduled hematology assessments) out to 96 hours post.

All SAD Cohorts will follow a sentinel design. On the first day of dosing only 2 (sentinel) subjects will be dosed. The randomization schedule will be constructed such that 1 of the subjects dosed on the first day will receive PDM608 and 1 will receive placebo. After review of the safety data from the 72 hours post-dose period the Investigator will decide whether to proceed with dosing the remaining subjects in the cohort (main group; 5 subjects randomized to receive PDM608 and 1 subject randomized to receive placebo).

Following completion of each cohort the safety and tolerability assessments through 96 hours post-dose (Day 5) will be reviewed by the SAC to determine whether to progress to the next dose level and the dose level for the next cohort, with a maximum 3-fold increase in dose level between SAD cohorts.

Following dosing of at least 3 SAD cohorts, the SAC will also decide whether to progress to MAD Part 2 of the study and, if so, on the starting dose for the first MAD cohort. Part 2 may be dosed in parallel with Part 1, but the decision to proceed to Part 2 can only be made following interim review of safety and tolerability data from doses through SAD Cohort 3. Full details of the interim data reviews are provided in [Section 8.2](#).

**Table 2 Description of Dosing: Part 1 Single Ascending Doses**

[figure not shown]
SAD Cohort	Investigational Medicinal Product	Dose a, b
1	PDM608 or matching placebo	350 µg
2	PDM608 or matching placebo	1050 µg
3	PDM608 or matching placebo	3150 µg
4	PDM608 or matching placebo	6300 µg
5	PDM608 or matching placebo	12600 µg

Details of the IMP are provided in [Section 5.2](#).

a Anticipated doses. The actual doses to be administered in this study will be determined following interim review by the SAC.

b Administration detailed in the Pharmacy Manual.

Each cohort will follow the same study design ([Figure 1](#)), detailed in the Schedule of Assessments ([Appendix 2](#)).

**Figure 1 Study Sequence: Part 1 Single Ascending Doses****8.1.2 Study Plan: Part 2 Multiple Ascending Doses**

Part 2 is a double-blind, randomized, placebo-controlled assessment of SC PDM608 MAD administrations. Subjects will be enrolled sequentially into 1 of up to 4 cohorts, each containing 12 subjects. Within each cohort, 9 subjects will be randomly assigned to receive PDM608 and 3 subjects will be randomly assigned to receive matching placebo. MAD Cohort 4 is optional; the decision on whether to dose this cohort will be based on interim review of preceding MAD Cohorts 1 to 3.

Part 2 may be dosed in parallel with Part 1, but can only proceed following interim review of safety and tolerability data from at least the first 3 SAD cohorts in Part 1. Dosing for each MAD cohort will be at a dose level 2-3 fold lower than the highest SAD cohort dose deemed safe by the SAC at the time of each MAD cohort initiation.

An evaluable subject for Part 2 is defined as a subject who has received all 4 doses of IMP and undergone all safety and tolerability assessments out to 96 hours post-final dose (dose 4). Sentinel dosing is not planned for MAD cohorts, but the SAC may implement a sentinel design if deemed appropriate.

Following completion of each cohort, the safety and tolerability assessments out to 96 hours post-final dose (Day 26) will be reviewed to determine whether to progress to the next dose level and the dose to be administered. Full details of the interim data reviews are provided in [Section 8.2](#).

**Table 3 Description of Dosing: Part 2 Multiple Ascending Doses**

MAD Cohort	Investigational Medicinal Product	Dose a, b	Dosing Schedule
1	PDM608 or matching placebo	XX µg	Once weekly for 4 weeks
2	PDM608 or matching placebo	XX µg	Once weekly for 4 weeks
3	PDM608 or matching placebo	XX µg	Once weekly for 4 weeks

4 (optional) c	PDM608 or matching placebo	XX µg	Once weekly for 4 weeks
------------------------------	----------------------------	-------	-------------------------

Details of the IMPs are provided in [Section 5.2](#).

[figure not shown]
a MAD cohort dose levels will be determined following interim review by the SAC.

b Administration detailed in the Pharmacy Manual.

c The decision on whether to dose MAD Cohort 4 will be based on interim review of preceding MAD Cohorts 1 to 3.

Each cohort will follow the same study design (Figure 2), detailed in the Schedule of Assessments ([Appendix 3](#)).

